## **5. Specific Aims:**

**Specific Aim. Evaluate the feasibility, reliability, and clinical effects of VTS on basic tasks of motor control and on the motor symptoms of patients with movement disorders.**

Hypothesis: VTS will produce beneficial effects on basic tasks of motor control and abnormal motor symptoms in patients with movement disorders. VTS Settings will include continuous stimulation between 60-120 Hz, intermittent stimulation at  $\frac{1}{2}$  baseline step frequency during walking, and sham stimulation (2 seconds of 30 Hz stimulation only at stimulation onset).

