## **6. Research Plan:**

### **6.1 Design Overview:**

This cross-sectional pilot study aims to identify the optimal device settings and preliminarily test the efficacy of the Not Impossible VibroHealth device in improving basic measure of motor control and symptoms in patients with PD and other movement disorders in the off-medication state. After informed consent, screening, and recruitment, the effects of VTS will be evaluated on basic tests of motor control and common movement disorders symptoms.

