## 6.5 Device Description and Previous Studies

The Vibrohealth system consists of 4 vibrating devices on bands and a magnetic contact charger (**Figure 1**). The devices are paired with a cell phone application (to be used solely by research investigators) that adjusts the parameters of vibratory stimulation during research visits (**Figure 2**).

The device consists of an actuator/sensor that, when placed against the surface of the skin, produces a vibrotactile sensation (vibration) through rapid lateral (side to side) motion. The intensity of the vibration produced by the Vibrohealth device is far less than that produced by commercially available massagers that provide vibratory stimulation for relaxation using similar technology. The sensor in the device is a tri-axial accelerometer and gyroscope that measures position using the same technology as smartphones.

A previous version of the Vibrohealth device was evaluated in 2017-2018 on 52 patients with PD and resting tremor at the Mount Sinai Hospital in New York City in a study funded by the device developer (Not Impossible). The Vibrohealth device was deemed

a nonsignificant risk device and was approved by full board IRB review (IRB #17-00555). There were no adverse events in any subjects receiving VTS. However, the stimulation setting intended to serve as a sham control setting (low amplitude continuous vibration) appeared to reduce resting tremor in approximately 60% of patients, suggesting that the vibration settings used in the protocol were inadequately investigated prior to study design. Though this study is being prepared for publication by the authors at Mount Sinai Hospital as a safety and feasibility study, the Parkinson

Foundation has decided to fund further pilot testing to ensure that any future clinical trials aimed at testing the efficacy of VTS are planned appropriately. We have tested the Vibrohealth device on 7 patients during our initial pilot testing since IRB approval without any adverse events.

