#### Baseline testing:

MDS-UPDRS: Select measures from the motor section of the Movement Disorders Society Unified Parkinson's Disease Rating Scale (MDS-UPDRs). The MDS-UPDRS is a revision of the Unified Parkinson's Disease Rating Scale (UPDRS) originally developed in the 1980s. The scale is used in the clinic as well as in research to measure PD symptom severity. Individual measures are rated as 0 (normal) to 4 (severe).

Montreal Cognitive Assessment (MoCA): The MoCA is a cognitive screening test designed to assist Health Professionals in the detection of mild cognitive impairment and dementia. It will be used to exclude patients with cognitive impairment significant enough to confound the research variables of interest.

6.7a: Outcomes to be measured in subjects with PD:

Quantitative Tremor Assessment: An external accelerometer (Delsys Trigno; <https://delsys.com/trigno/>) will be adhered to the skin of the dorsum of the hand and will be used to quantify displacement of the hand due to tremor in the settings listed below. Delsys Trigno sensors have been used in multiple prior UF IRB approved studies and is FDA and CE registered with FCC ID, and is certified IEC601-1 (General Requirements for Medical Devices) and IEC601-1-2 (electromagnetic compatibility requirements for Medical Devices) with a UL recognized Internal Battery.

- 1. Sitting at rest
- 2. Sitting with both arms outstretched
- 3. Sitting at rest while performing a distracting cognitive task (reciting the months of the year backwards)
- 4. Transition from rest to posture (arms held directly in front of patient) for 10 seconds

Kinesia One accelerometer: The following select measures of MDS-UPDRS Part III: Motor Examination will be repeated before and during VTS:

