## **7. Outcome and Statistical Approaches:**

For essential tremor and dystonia, the aims of this unblinded pilot study are to identify the optimal settings of VTS that are most promising to be tested in future clinical trials, statistical analysis will be limited to basic measures of central tendency. We will compare scores and values on the individual outcome measures listed above both on and off VTS, and within disease group means for each measure will be used to help guide the choice of settings to be tested in future studies. This pilot study will not be powered for between disease groups analysis or to test the efficacy of VTS for ET, or dystonia.

For Parkinson's disease, we expect to have data sufficient to justify exploratory statistical analysis. We have estimated that the number of patients included will allow for statistical analysis of patient's task performance before and during VTS. This was based on a medium effect size (Cohen's  $d = 0.50$ ) for the comparison of tremor power during VTS versus baseline. With an alpha of 0.05 and power of 0.80, the required sample size is 27 (based on a one-sided paired sample t-test). Thus, by recruiting 30 participants with PD, our sample size will give us sufficient statistical power to detect an effect with medium effect size. Statistical analysis will consist of a repeated measures ANOVA on the change in tasks performance scores relative to baseline. All post-hoc analyses will be corrected for multiple comparisons using Bonferroni correction.

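### The power claimed for PD belongs to a one-sided VTS-versus-baseline test, whereas the planned ANOVA compares settings; active versus sham is neither named nor powered

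*Combined protocol and SAP*

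**What the plan says.** Section 7 bases the PD sample size on Cohen's d = 0.50 "for the comparison of tremor power during VTS versus baseline", with alpha 0.05, power 0.80 and a one-sided paired t-test. This gives 27 patients. It plans to recruit 30 and concludes that "our sample size will give us sufficient statistical power to detect an effect with medium effect size".

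The analysis is then described separately: "Statistical analysis will consist of a repeated measures ANOVA on the change in tasks performance scores relative to baseline". Multiplicity is covered by one sentence: "All post-hoc analyses will be corrected for multiple comparisons using Bonferroni correction". Section 7 does not list the levels of the ANOVA, the post-hoc contrasts or their number, and it does not mention sham.

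Sham appears in Section 5, where the VTS settings are continuous stimulation at 60-120 Hz, intermittent stimulation at half the "baseline step frequency during walking, and sham stimulation (2 seconds of 30 Hz stimulation only at stimulation onset". Section 6.1 says that the study will "preliminarily test the efficacy of the Not Impossible VibroHealth device". Section 6.7 describes the tests as done on and off VTS, and for the Kinesia measures says "Motor Examination will be repeated before and during VTS".

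Section 6.5 reports that in an earlier study the setting "intended to serve as a sham control setting (low amplitude continuous vibration) appeared to reduce resting tremor in approximately 60% of patients".

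**The concern.** Two things do not line up. First, the power statement comes from a test that is not the planned one. A one-sided paired t-test of during versus before asks whether tremor changes at all under VTS. An ANOVA on changes from baseline asks whether the change differs between settings, and its F test has no direction. The power of one does not carry over to the other.

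Second, the comparison that is sized cannot identify a stimulation effect. A patient who does better because of expectation, or because the task is being repeated, contributes to a VTS-versus-baseline difference just as a true responder does. The plan already lists a control setting that could address this, and Section 6.5 shows that response under an intended sham is a live issue for this device. Yet the active-versus-sham contrast is unnamed and has no stated sidedness, number of tests or power. A reader of Section 7 could take the quoted power as applying to an effect beyond sham.

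**Working it through.** **Inputs.** From Section 7: d = 0.50, one-sided alpha 0.05, power 0.80, required n = 27, planned n = 30. From Section 5: settings continuous, intermittent (tied to walking) and sham. Assumed, because the documents give no values: change-from-baseline scores with SD 1 under each setting; correlation r between a patient's change scores under two settings of 0.5, range 0.3 to 0.7; net active-over-sham effect of 0.5 SD, chosen to match the plan's own d.

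**Step 1: the plan's figure.** Paired t power is P(T > t crit), with T noncentral t on n − 1 degrees of freedom and noncentrality d√n. With d = 0.5 and one-sided 0.05, power is 0.798 at n = 26, 0.812 at n = 27 and 0.848 at n = 30. The stated 27 is reproduced, so the arithmetic is sound for VTS versus baseline.

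**Step 2: two levels (continuous, sham).** These are the listed settings that fit tremor, since intermittent stimulation is defined by walking. With two levels, F is the square of the paired t on active minus sham, so it is a two-sided test. The SD of the difference is √(2(1 − r)), and the standardised effect is 0.5 divided by it.

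| r | SD of difference | standardised effect | noncentrality (× √30) | power |
|---|---|---|---|---|
| 0.3 | 1.183 | 0.423 | 2.315 | 0.61 |
| 0.5 | 1.000 | 0.500 | 2.739 | 0.75 |
| 0.7 | 0.775 | 0.645 | 3.536 | 0.93 |

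At r = 0.5 the noncentrality equals that of the sizing test (0.5 × √30 = 2.739). The fall from 0.85 to 0.75 is therefore due wholly to two-sided testing. At a net effect of 0.3 SD the same calculation gives 0.27, 0.36 and 0.54.

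**Step 3: three levels (continuous, intermittent, sham).** Simulation, 40,000 runs per case, n = 30: F at 0.05, then three two-sided pairs with Bonferroni (alpha 0.05/3 each).

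| True pattern of changes | r = 0.3 | r = 0.5 | r = 0.7 |
|---|---|---|---|
| One active setting 0.5 above sham, other equal to sham: that setting found | 0.42 | 0.58 | 0.83 |
| Both active settings 0.5 above sham: at least one found | 0.57 | 0.74 | 0.93 |

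**Step 4: error rate when sham is a level.** When no active setting beats sham, the same procedure declares one better in 0.8% to 1.4% of runs. This covers two patterns: all three settings shifted by 0.5, and continuous and sham both shifted by 0.5 with intermittent at 0.

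**Step 5: what the sized contrast responds to.** Suppose stimulation has no specific effect but there is a non-specific shift from baseline (assumed). The one-sided test at n = 30 is then significant 28% of the time for a shift of d = 0.2, 48% for 0.3 and 85% for 0.5. These rates describe the sizing test only.

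**The case against.** The strongest reply is that sham is obviously in the analysis. The sole Specific Aim lists it as a setting, and an ANOVA on change scores needs at least two non-baseline conditions. For tremor, the listed settings that fit are continuous and sham. On that reading active versus sham is tested with error well controlled (Step 4), and failing to list the levels is only missing detail. This stands. A reader might infer from the silence of Section 7 that the trial has no sham-controlled comparison. That is possible, but it is the least natural reading and the documents do not establish it.

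A reader might also take the 28% to 85% in Step 5 as the plan's false-positive rate. They are not: the planned analysis is the ANOVA, and the t-test appears only in the sizing. Nor can the 60% in Section 6.5 be turned into an expected sham response here. That sham was continuous low-amplitude vibration, unlike the present brief pulse at onset, and the plan does not define what counted as a reduction.

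It is also fair to say that the power shortfall depends on assumptions. It is modest with two levels, and it disappears at a correlation of 0.7. The study is a pilot, its PD analysis is called exploratory, and identifying settings comes first among its aims.

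The mismatch itself remains. The sufficiency claim rests on a test that is not the planned one, and the contrast best suited to a preliminary look at efficacy is unnamed and unpowered.

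**Conclusion.** The point holds as a mismatch between the sizing and the analysis, not as an arithmetic error or a missing control. Power for the planned comparison of settings is below the 0.80 target at a net effect of 0.5 SD, unless the between-condition correlation is high. The two-level figure is the one that fits tremor; the three-level figures apply only to tasks on which both active settings and sham are given.

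All the ranges rest on an assumed SD of 1, correlations of 0.3 to 0.7, and a net effect as large as the plan's before/during effect. An effect net of sham may well be smaller, which would lower the power further. That Section 7 omits the contrast is certain; the size of the consequence is not. For an exploratory pilot the severity is minor to moderate.

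**What to change.** In Section 7:

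- List the ANOVA levels for each PD task, including sham wherever it is given.
- Name within-patient active minus sham as the lead PD contrast, still exploratory, with its sidedness and the number of tests under Bonferroni.
- Report active minus baseline and sham minus baseline as descriptive.
- Say that N was derived only for VTS versus baseline, and restate power at n = 30 for the sham contrast. For example, with a standardised paired difference of 0.5, one pre-named one-sided test has power 0.85, two with Bonferroni 0.75, and one two-sided test 0.75.

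The cost is a few sentences, with no added patients or visits. The downside is a less favourable power statement. Two conditions must hold for the contrast to do its job. Sham has to be given on the tested PD tasks, which Section 5 does not confirm. The order of settings also has to be balanced, because otherwise active minus sham still carries retest effects. The documents state no order, so Section 6.7 should give one.

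### The PD sample size is powered for a single one-sided VTS-versus-baseline t-test, but Section 7 lists a repeated measures ANOVA with Bonferroni-corrected post-hoc tests, for which power is not shown

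*Combined protocol and SAP*

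**What the plan says.** Everything needed is in the PD paragraph of Section 7 (Outcome and Statistical Approaches), with the settings in Section 5 (Specific Aims).

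- **Purpose of the sample size.** The number of PD patients is meant to support analysis of "task performance before and during VTS".
- **Sizing test.** A medium effect, Cohen's d = 0.50, is assumed "for the comparison of tremor power during VTS versus baseline". Then: "With an alpha of 0.05 and power of 0.80, the required sample size is 27 (based on a one-sided paired sample t-test".
- **Power claim.** With 30 PD patients, "our sample size will give us sufficient statistical power to detect an effect with medium effect size".
- **Listed analysis.** "Statistical analysis will consist of a repeated measures ANOVA on the change in tasks performance scores relative to baseline".
- **Multiplicity.** "All post-hoc analyses will be corrected for multiple comparisons using Bonferroni correction". Neither the number of these tests nor their sidedness is given.
- **Settings.** Section 5 says "VTS Settings will include continuous stimulation between 60-120 Hz", and adds intermittent stimulation at half the "baseline step frequency during walking", and sham. The number of continuous frequencies is not given.
- **Tremor conditions.** Section 6.7a measures tremor in four conditions. Section 7 does not say which of them d = 0.50 refers to.
- **Status.** Section 7 describes the PD analysis as exploratory.

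**The concern.** The paired t-test appears only as the basis for the sample size. The analysis that follows differs from it in three respects.

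1. **Contrast.** The sized test compares VTS with baseline. In an ANOVA on change scores, baseline has already been subtracted, so the setting effect asks whether the settings, sham included, differ from one another.
2. **Direction.** The sized test is one-sided. The ANOVA F-test has no direction.
3. **Alpha.** The sized test uses the full 0.05. A Bonferroni correction over two or more comparisons uses less.

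A reader therefore cannot attach the 80% to any test that the plan lists. Section 6.1 says the study should find the best settings and give a preliminary test of efficacy, and Section 6.5 says it should help future trials to be planned properly. A null result read as coming from a test with 80% power, when the test actually run had less, could lead to a setting being dropped wrongly.

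**Working it through.** **Inputs from Section 7:** d = 0.50, alpha 0.05, target power 0.80, one-sided paired t-test, 30 PD patients recruited.

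**Input not in the documents:** the number k of Bonferroni-corrected post-hoc tests. I assume k = 2 and k = 3. Three equals the number of setting types in Section 5 (continuous, intermittent, sham). Two applies if intermittent stimulation, which Section 5 ties to walking, is not used in the tremor tasks.

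**Formula.** For a paired t-test with n patients, df = n − 1 and the noncentrality is d × √n. One-sided power is P(T > t_crit), where T is noncentral t and t_crit is the 1 − alpha quantile of central t. For a two-sided test alpha is halved in the quantile and the opposite tail is added, which is negligible here. For Bonferroni, alpha is 0.05/k.

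**Step 1: reproduce the plan's figure (one-sided, alpha 0.05).**

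| n | d × √n | t_crit | Power |
|---|---|---|---|
| 26 | 2.550 | 1.708 | 79.8% |
| 27 | 2.598 | 1.706 | 81.2% |
| 30 | 2.739 | 1.699 | 84.8% |

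The smallest n that reaches 80% is 27, as stated.

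**Step 2: the same VTS-versus-baseline contrast as a corrected post-hoc test.** Here n = 30 and the noncentrality is 0.50 × √30 = 2.739.

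| Sidedness | k | alpha per test | t_crit (df 29) | Power at n = 30 | n for 80% |
|---|---|---|---|---|---|
| One-sided | 2 | 0.0250 | 2.045 | 75.4% | 34 |
| One-sided | 3 | 0.0167 | 2.234 | 69.2% | 38 |
| Two-sided | 2 | 0.0250 | 2.364 | 64.7% | 41 |
| Two-sided | 3 | 0.0167 | 2.541 | 58.3% | 45 |

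All four are below 80%. A single uncorrected two-sided test at n = 30 has 75.4% power. The last column shows the size of the gap and is not a proposal to recruit more patients.

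**Step 3: the ANOVA setting effect.** Its power depends on the number of settings, the pattern of mean changes across them (including any sham effect) and the correlation between change scores. The documents give none of these except the types of setting, so I give no figure.

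**The case against.** **The calculation is correct.** A reader might infer from the mismatch that 27 is an arithmetical error. It is not: the figure reproduces exactly for the test named.

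**The baseline comparison is not ruled out.** Section 7 names it in the sizing sentence, and the ANOVA uses change from baseline, so a test of mean change against zero fits the same data. This stands. What is missing is a line that lists this test and says how it relates to the ANOVA and to the Bonferroni correction.

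**No shortfall is demonstrated.** A reader might infer that the study is underpowered. The documents do not support that. The figures below 80% for corrected tests need VTS versus baseline to be one of two or more such tests, and the plan does not say it is. The choice of three is also open to dispute: it counts sham as one of the comparisons with baseline, and it counts a setting tied to walking. If there is one one-sided test, 84.8% holds. Nor can low power be claimed for the ANOVA, because it cannot be computed from what is given.

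**This is an exploratory pilot.** True, and it limits the consequence. The plan nevertheless chose to claim sufficient power, and that claim should belong to a stated test.

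**Conclusion.** The concern holds as a mismatch between the sizing test and the listed analysis, together with missing detail on the post-hoc tests. The power claim is supported for one comparison only: a single one-sided, uncorrected test of tremor power during VTS against baseline, with 84.8% power at n = 30. It is not shown for the analysis that Section 7 lists.

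If the baseline comparison is made as one of 2 or 3 corrected post-hoc tests, the loss against the 84.8% is 9.4 or 15.6 percentage points one-sided (84.8 − 75.4; 84.8 − 69.2), and 20.1 or 26.5 two-sided (84.8 − 64.7; 84.8 − 58.3). These figures rest on the plan's d = 0.50, on 30 patients with complete data, and on the assumed number of comparisons. More comparisons would lower power further.

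This limits the power statement. It does not invalidate the study or show that 30 patients are too few for an exploratory pilot. It should be fixed.

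**What to change.** Keep 30 PD patients and restate the power sentence in Section 7, for example:

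> The 80% power (27 required; 85% with 30) applies only to a single one-sided, uncorrected comparison of tremor power during VTS versus baseline at d = 0.50. It does not cover the repeated measures ANOVA setting effect or the Bonferroni-corrected post-hoc tests. For a VTS-versus-baseline post-hoc test, 30 patients give 75% / 69% (one-sided) or 65% / 58% (two-sided) power with 2 / 3 comparisons.

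Once the investigators have fixed the number and sidedness of the post-hoc tests, the last sentence can be cut to the one figure that applies.

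**Optional.** If the investigators want the 85% to stand for a planned test, they can list the single comparison as an analysis in its own right. This would commit them in advance to one setting and one tremor condition, in a study that also aims to find the best settings. The comparison has no sham control, so it should be reported beside the ANOVA. Which setting and condition to name is for the investigators.

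**Cost.** Text only, with no added patients or procedures. The downside is a less favourable power statement.

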### **6.2 Participants:**

We will recruit 30 patients with PD who are between the ages of 18-80 years old and independently living in the community. Will additionally recruit up to 5 patients with ET and up to 5 patients with dystonia. To account for screening failures or patients who cannot tolerate the sensory stimulation, we anticipate screening and consenting ~50 individuals.

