### **6.7 Duration of Study and Overview of Procedures and Protocol:**

Testing will occur over the course of a single day at the Fixel Institute for Neurological Diseases. Similar to new patient clinical evaluations, subjects will be instructed to withhold any PD, ET, or dystonia medications for 12 hours prior to testing. The study visit will last up to 4 hours and will include a variety of motor tasks and clinical tests (described in detail below) both on and off VTS. For Parkinson's disease and essential tremor patients, the devices will be worn on the wrist and/or ankles. For patients with dystonia, the devices will be adhered to the skin of the neck using medical grade double sided tape and a latex medical wrap. Patients with PD will undergo a more comprehensive testing evaluation, while patients with ET or dystonia will undergo a brief, more focused evaluation. Subject responses will not be compared across diseases given the preliminary nature of the research and analysis. Outcomes to be measured are described below in the order that they will be tested for each individual subject group (PD, ET, dystonia).

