## **8. Methodological Limitations and Potential Challenges:**

Potential challenges that may occur during the study include subject discontinuation prior to completion of data collection due to boredom or irritation of the skin from vibration.

Partial collected data will still be useful in helping to guide the choice of simulation

parameters in future clinical trials to test the potential of VTS as an adjunctive therapy to improve motor control or reduce the symptoms of PD, ET, or dystonia.

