### **10. Possible Discomforts and Risks:**

In general, the risks are minimal for individuals who participate in this study. As the intensity of the vibration produced by the Vibrohealth device is far less than that which is produced by commercially available massagers that provide vibratory stimulation to the body, the incidence and severity of any adverse effects is expected to be limited, and no adverse events occurred in a previous trial using the Vibrohealth device in over 50 patients with PD and in our pilot testing at UF of 8 subjects. With regard to discomforts and risks, first the VTS stimulation could be annoying or unpleasant, and there is the possibility of minor skin irritation at the site where the wearable devices are placed.

Second, subjects will be asked to come to testing sessions OFF medications (as is done during standard-of-care initial clinic visits) in order to reduce confounding effects of medications, which could be temporarily uncomfortable. Third, patients may also find the tasks and scales tedious or boring. To minimize fatigue associated with completion of screening and tasks, subjects will be allowed to take frequent breaks to rest as needed. Patients will have the option of discontinuing testing at any time, and data that is partially collected may still be useful given the preliminary nature of the study. Though unlikely, it is possible skin irritation might persist outside of the testing period. Should this occur, the patient would be instructed to seek routine medical care. It is also possible that there are unknown risks for participating in this study.

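### The repeated measures ANOVA named for PD, in its classical form, drops a patient who misses one setting, although early stopping is foreseen and partial data are called useful

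*Combined protocol and SAP*

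**What the plan says.** Section 7 states for PD: "Statistical analysis will consist of a repeated measures ANOVA on the change in tasks performance scores relative to baseline", with Bonferroni correction of post-hoc comparisons. It names no within-patient factor, number of levels, analysis set or rule for missing values. The sample size in the same section (27 required, 30 recruited) comes from a one-sided paired t-test of tremor power during stimulation against baseline. Descriptive-only analysis is reserved for essential tremor and dystonia.

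Other sections bear on this:

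- **Section 5** lists continuous stimulation, intermittent stimulation and sham. It ties the intermittent setting to walking: "baseline step frequency during walking, and sham stimulation".
- **Section 6.2**: "To account for screening failures or patients who cannot tolerate the sensory stimulation, we anticipate screening and consenting ~50 individuals".
- **Section 6.7**: "Outcomes to be measured are described below in the order that they will be tested". In 6.7a tremor comes first ("Quantitative Tremor Assessment: An external accelerometer"), and the timed-up-and-go (TUG) is the last performance task.
- **Section 8** foresees "subject discontinuation prior to completion of data collection due to boredom or irritation of the skin from vibration" and adds: "Partial collected data will still be useful in helping to guide the choice of simulation".
- **Section 10** allows patients to stop at any time and says "data that is partially collected may still be useful given the preliminary nature of the study".

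**The concern.** A classical repeated measures ANOVA needs a value at every level of the within-patient factor. A patient who completes two of three settings and then stops leaves the analysis of that outcome, and the contrast that patient did complete goes too. One aim of the study (Section 6.1) is to identify the best device settings, and Section 8 says partial data should serve that purpose. The only PD method named would discard some of those data.

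Two things are at stake. The first is precision, because fewer patients contribute to every contrast. The second is bias: if stopping is related to response, those who finish are a selected group. Skin irritation from the vibration, one of the two reasons Section 8 gives, is produced by the intervention. The documents do not show that it tracks response.

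The problem arises only where a patient has some but not all settings for an outcome. Three settings apply most clearly to TUG, which comes late; seated tasks may have only continuous and sham. Tremor, the outcome used for sizing, is tested first and is least exposed. The plan does not say whether settings are run within each task or all tasks within each setting.

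**Working it through.** **1. The plan's own figure.** One-sided paired t-test, d = 0.50, alpha 0.05 (Section 7). Power is the upper tail of a noncentral t with n − 1 degrees of freedom and noncentrality 0.50√n, beyond the 95th percentile of the central t.

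| Complete patients | 30 | 27 | 26 | 24 | 21 |
|---|---|---|---|---|---|
| Power | 0.848 | 0.812 | 0.798 | 0.768 | 0.715 |

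The smallest n reaching 0.80 is 27, as stated. The margin is 30 − 27 = 3 patients. This is one comparison against baseline. It shows how losing complete patients lowers power; it is not the power of the ANOVA.

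**2. The ANOVA with three settings.** Assumed mean changes are 0.5 (A, first active), 0 (S, sham) and 0.5 (B, last active), with residual variance 0.5, so a paired difference has SD √(2 × 0.5) = 1. The grand mean is 1/3 and the squared deviations sum to 1/36 + 1/9 + 1/36 = 1/6. Noncentrality is n × (1/6)/0.5 = n/3, that is 10, 9, 8 and 7 for n = 30, 27, 24 and 21. With 2 and 2(n − 1) degrees of freedom under sphericity, omnibus power is 0.79, 0.74, 0.69 and 0.62.

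**3. Power by method.** Simulation with 4,000 runs per cell (Monte Carlo standard error at most √(0.25/4000) = 0.008), n = 30, patient variance 1, residual variance 0.5. Setting B is missing at random in 10/20/30% of patients, and tests are two-sided at 0.05/3. The mixed model is REML with compound symmetry and Kenward-Roger degrees of freedom.

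| Contrast | Completers | Available-pair t-tests | Mixed model |
|---|---|---|---|
| A − S (all completed) | 0.55/0.49/0.43 | 0.58/0.58/0.58 | 0.60/0.60/0.60 |
| B − S (B partly missing) | 0.56/0.50/0.43 | 0.53/0.47/0.40 | 0.58/0.54/0.48 |

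With nothing missing, ANOVA and mixed model both give 0.60 (A − S) and 0.62 (B − S).

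With two settings (two-sided 0.05), completers have 0.71/0.64/0.58 and the mixed model 0.71/0.66/0.60, a gain of 0.00 to 0.02.

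**4. Bias when stopping depends on the observed A − S benefit.** Let a share q stop, with probability 1.6q below the mean benefit and 0.4q above it (a four-fold ratio). The mean of a half-normal is √(2/π) = 0.798, so the completer mean is

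0.5 + 0.798 × ½ × [(1 − 0.4q) − (1 − 1.6q)]/(1 − q) = 0.5 + 0.479 q/(1 − q).

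For q = 0.1, 0.2, 0.3 this is 0.553, 0.620, 0.705. Simulation gave 0.556, 0.621, 0.706. A − S and B − S share sham and correlate 0.5, so the shift in B − S is half as large.

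| Estimate of a true 0.50 | Completers | Available pairs | Mixed model |
|---|---|---|---|
| A − S, four-fold | 0.56/0.62/0.71 | 0.50 | 0.50 |
| B − S, four-fold | 0.53/0.56/0.60 | 0.53/0.56/0.60 | 0.50 |
| A − S, two-fold | 0.53/0.57/0.61 | not tabulated | 0.50 |

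Available pairs cannot help B − S, because its pairs are the completers. With two settings and a four-fold ratio on the first setting's change, completers give 0.52/0.54/0.58 and the mixed model 0.49 to 0.50.

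**5. Where the mixed model falls short.** If stopping depends on the unobserved B − S, completers estimate B − S as 0.55/0.62/0.71 and the mixed model as 0.53/0.58/0.65.

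**6. Checks.** Under the null with 30% missing, the mixed model rejects in 0.044 (A − S) and 0.049 (B − S) of runs at 0.05. On a complete data set, ANOVA and mixed model both give t = 2.186 on 58 degrees of freedom.

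**The case against.** The strongest reply is that exclusion is inferred, not written. Section 7 does not mention deletion, and Sections 8 and 10 do not promise that partial data enter the ANOVA; descriptive means by setting would make use of them. That stands: this is a tension, not a contradiction. But Section 7 offers no descriptive or other alternative for PD, so the named method is all the reader has.

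Second, the stopping rates have no source in the documents and may be too high. Testing is one visit of up to four hours with breaks, Section 6.5 reports no adverse events in 52 earlier patients, and about 50 consents are planned for at most 30 + 5 + 5 = 40 patients. That also stands and is why only a range is given. Section 6.2 states no replacement rule, however, and replacement would restore numbers without using the partial data or removing selection.

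Third, if settings run within each task, a patient who stops has at most one partly complete outcome, and later outcomes have no stimulated value to recover. This is correct, and there the gain is nil.

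Fourth, the reasons given for stopping are boredom and irritation, not poor response, so the bias mechanism is hypothetical. That stands too; the bias figures show what could happen, not what is expected.

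Finally, the simulated within-patient correlation, 1/1.5 = 0.67, was not varied, and the simulated active change from baseline is 0.5/√1.5 = 0.41 SD, not the plan's 0.50. With two settings, known variances and missing share q, the mixed model reduces variance by q(1 − ρ)/2. At q = 0.2 that is 1% for ρ = 0.9, 3.3% for 0.67 and 7% for 0.3. The two-setting gain is small throughout.

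**Conclusion.** The concern holds and is minor; confidence is medium because the run order, the number of settings per task and the stopping rate are not stated. For a three-setting outcome with 10 to 30% of patients missing only the last setting at random, restricting to completers costs 0.05 to 0.17 in power for the contrast everyone completed (0.60 against 0.55 to 0.43) and 0.02 to 0.05 for the other. Bias appears only if stopping is related to response. For two-setting outcomes the difference is close to nothing, and for tremor, tested first, exposure is lowest. The case for change rests mainly on its low cost: the alternative ordinarily gives the same setting tests when data are complete and balanced, and uses more of the data when they are not.

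**What to change.** In Section 7, replace the repeated measures ANOVA with a linear mixed model on change from baseline for each continuous or scored PD task outcome. Use setting as a fixed effect, patient as a random effect, every setting a patient completed, Kenward-Roger degrees of freedom and the same Bonferroni correction. Include test order only if the order of settings varies between patients. Analyse CGI-I as rated, without subtracting a baseline, since it is already an assessment against baseline. Report the number of patients per setting and outcome, with reasons for stopping.

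The cost is two or three sentences, standard software and slightly more analysis work. The model assumes data are missing at random, only partly corrects bias if stopping depends on unobserved response, and cannot recover a patient with no stimulated value on an outcome. An available-pair rule for post-hoc tests would be simpler, but for contrasts involving the partly missing setting it has less power and keeps the completer bias.
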